6.1 Intent-To-Treat Analysis Set

All randomized (as planned) subjects will be included in the ITT analysis set.

6.2 Full-Analysis Set

All randomized subjects who are included in the ITT analysis set and received at least 14 days of study drug for pituitary priming will be included in the FAS.

6.3 Modified Intent-To-Treat Analysis Set

All randomized subjects who received at least one pulsatile injection delivery of study drug will be included in the mITT Population.

6.4 Per Protocol Analysis Set

All subjects who are included in the FAS and did not have exclusionary major protocol deviations will be included in the PPS.

6.5 Safety Analysis Set

All subjects who received at least one pulsatile injection delivery of study drug will be included in the Safety Population. Subjects are analysed according to the actual treatment received.

Table 2 Treatment group variables vs. analysis set

		Treati	Treatment Variable Used in Analysis						
Analysis Set	Analysis Set Population Flag	Variable Label	Variable Name (Character)	Variable Name (Numeric)					
Intent-To-Treat Analysis Set	ITTFL	Planned Treatment	TRTP	TRTPN					
Full-Analysis Set	FASFL	Planned Treatment	TRTP	TRTPN					
Modified Intent-To- Treat Analysis Set	mITTFL	Planned Treatment	TRTP	TRTPN					
Per Protocol Analysis Set	PPROTFL	Planned Treatment	TRTP	TRTPN					
Safety Analysis Set	SAFFL	ActualTreatment	TRTA	TRTAN					

Date: 07 Dec 2017 E-Statistical Analysis Plan-21977; Ver.1.0 Supersedes: None Page 16 of 59

7 Trial population

7.1 Demographics and Other Baseline Characteristics

A summary of demographics and other baseline characteristics will be presented for the subjects in the FAS by treatment group. No statistical testing for baseline differences will be performed.

Categorical (discrete) data will be summarized using numbers and percentages. The percentages will be based on the total number of subjects with a corresponding assessment. Continuous data will be presented, for example, using the number of subjects (N), mean and standard deviation, median, minimum and maximum. All baseline characteristics will be listed.

7.1.1 Demographics

Descriptive statistics of baseline demographics variables (e.g., age, race and ethnic origin, height, weight and BMI) will be summarized for the subjects in the FAS by treatment group.

7.1.2 Vital Signs at Baseline

Baseline vital signs will be summarised in the FAS by treatment group.

7.1.3 Laboratory Efficacy/Pharmacodynamic Parameters at Baseline

Baseline assessments of safety laboratory tests (haematology, chemistry and urinalysis) and other laboratory tests (urine pregnancy, LH, FSH, E2, P4) will be summarized for the subjects in the FAS by treatment group. The baseline values for all laboratory/pharmacodynamics parameters will be the values obtained at the last assessment prior to the first dose of IMP.

7.2 Medical History

Medical and gynecologic history recorded at screening visit will be coded using the Medical Dictionary for Regulatory Activities (MedDRA) at the latest version available at the time of interim or final analysis, and will be listed and summarized by system organ class (SOC) and preferred term (PT).

7.3 Prior and Concomitant Medication

Prior and concomitant medication will be coded using World Health Organisation Drug (WHODrug) Dictionary version September 1, 2013 and summarised by anatomical-therapeutic-chemical (ATC) classification 1st level (alphabetically), ATC classification 2nd level (in decreasing order of frequency) and treatment group. These medications will be tabulated separately for:

- 1) Prior medication, i.e. medication taken exclusively prior to treatment (i.e. with stop date before date of first IMP administration);
- 2) Concomitant medication, i.e. medication taken during the treatment period (i.e. medication that was not stopped before date of first IMP-administration).

If the timing of the dose of a concomitant medication cannot be established in relation to the administration of IMP, it will be considered as concomitant medication. Concomitant medication

Page 17 of 59

will be subdivided into ongoing (started before first IMP administration) and treatment-emergent (starting after first IMP administration) concomitant medication.

7.4 Physical Examination

Statistical Analysis Plan

Subjects with abnormalities at any screening, baseline, or post-baseline visit will be listed with all physical examination evaluations.

Date: 07 Dec 2017 E-Statistical Analysis Plan-21977; Ver. 1.0 Supersedes: None Page 18 of 59

8 Exposure and Treatment Compliance

8.1.1 Extent of Exposure

The total duration of study treatment exposure defined as

Date of last OmniPod application – Date of first OmniPod application +3

will be summarized descriptively and listed for the Safety Population by treatment group.

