Follicular and endometrial development: Follow-up will begin on Day 10 of treatment. Follicular and endometrial development will be monitored by TVUS every other day or per the investigator's discretion (minimum of 3 TVUS), until a dominant follicle of ≥ 18 mm mean diameter and normal endometrium (thickness and pattern) are confirmed. If a dominant follicle ≥ 18 mm mean diameter is not observed after 21 full days of treatment, the therapy will be discontinued. However, the treatment may be continued for a maximum of 39 days at the discretion of the investigator if the patient has growing follicle(s). After Day 10, a single blood sample for E₂ assessment will be collected each time the subject returns for TVUS. A subject who has an increased risk of developing multiple gestation/OHSS (4 or more follicles with a mean diameter ≥ 15 mm by TVUS and E₂ levels ≥ 1200 pg/mL) will be discontinued from treatment.

LH surge detection with Clearblue® digital ovulation urine test ¹³ will begin when follicles with a mean diameter ≥ 14 mm are documented on TVUS. The Clearblue test will be administered daily, between 8 and 11 AM at approximately the same time each morning, until a positive test result occurs. Subjects should document the date of their first Clearblue test and the date of their first positive test result on the subject diary card ([Appendix II](#)). The subject should notify the site immediately once the surge has been detected to schedule a visit within 72 hours for confirmatory TVUS. Subjects will be advised to engage in sexual intercourse on the day of LH surge, the day following LH surge, and per investigator's discretion thereafter. The subject should also document the date(s) of sexual intercourse on the subject diary card.

If LH surge is not detected after 21 full treatment days, the subject will be discontinued. However, the treatment may be continued for a maximum of 39 days at the discretion of the investigator if the patient has growing follicle(s). The subject will be instructed to visit the site to return all study drug and the OmniPod System.

Blood samples for progesterone (P₄) levels: A single blood sample for P₄ will be taken on Day 1 (pre-treatment baseline) prior to dosing. Blood samples will also be obtained on Day 19, Day 21, Day 23, Day 25, and Day 27 after initiation of study drug. For subjects who have discontinued the study early and ended treatment on or after Day 14, a blood sample will also be taken at the End-of-Study Visit.

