5.6.2 Assessment of Compliance

The OmniPod will be applied at the study site on Treatment Day 1, Treatment Day 10, and Treatment Day 25 (if applicable). All other OmniPods can be applied by the subject either at home or at the study site. Subjects will be provided training and an instruction manual.

On Day 1 and at each study visit during treatment, the subjects will be monitored closely by the unblinded coordinator to ensure the medication is being delivered and the pump is functioning properly. The Manager records drug delivery data that may also be analyzed. The data in the Manager may be collected and recorded by the unblinded coordinator when the subject returns the Manager to the site.

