9.7 Extent of Exposure

The total study treatment exposure, measured by total duration (calculated by treatment start and stop dates/times), will be summarized and listed for the Safety Population by treatment group.

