8.1.2 Treatment Compliance

Summary (descriptive) statistics will be presented for the number of OmniPods applied by each patient and the treatment compliance during the patient's actual treatment period, defined as the actual days of treatment exposure divided by the patient's total treatment exposure duration. The actual days of treatment exposure is the sum of the durations of individual applications. For each OmniPod application, the duration is calculated as: date of next application — date of current application, or 3, whichever is smaller. For the last application, it is equal to 3.

.

9 Efficacy

A Bayesian adaptive design is adopted to address the following objectives:

- 1. Demonstrate superiority of the pooled middle and high doses over placebo
- 2. Evaluate the dose-response relationship

The adaptive design includes two interim analyses, conducted after approximately 9 and 12 patients per arm enrolling in the study, respectively. Each interim analysis provides opportunities for stopping the trial early due to efficacy success utilizing the group sequential strategy or due to efficacy futility through Bayesian predictive probability of success. Furthermore, it allows the low dose to be dropped following the interim look if it shows a much lower response rate compared with the middle and high doses.

Each interim analysis will result in one of the following outcomes:

- 1. Continue the trial with all arms
- 2. Continue the trial without the low dose
- 3. Declare early success, but continue the trial without placebo
- 4. Declare early success and stop the trial (both placebo and low dose dropped)
- 5. Stop the trial for futility

When the primary efficacy analysis is not successful at the interim analysis, and if the ovulation rate in the low-dose arm is sufficiently low, satisfying

$$R_{low} \le (R_{high+middle}) - 0.2, \tag{1}$$

then the trial will continue without the low dose, resulting in outcome #2 above. Note that R_{low} and $R_{high+middle}$ in the inequality (1) above are the observed ovulation rates in the low dose arm and the combined middle- and high-dose arms, respectively. However, if inequality (1) is not satisfied, then the trial will continue with all arms (outcome #1).

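### SAP 8.1 credits every last pod with 3 full days where Protocol 9.7 uses actual stop times, and neither document says how the 14 days for the FAS are counted

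*SAP*

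**What the plan says.** **Exposure.** SAP 8.1.1 defines total duration as "Date of last OmniPod application – Date of first OmniPod application +3" and says that it "will be summarized descriptively and listed for the Safety Population by treatment group". Protocol 9.7 has the same quantity "measured by total duration (calculated by treatment start and stop dates/times)".

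**Compliance.** SAP 8.1.2 divides actual days by the total duration. Each pod except the last counts as "date of next application — date of current application, or 3, whichever is smaller". The last pod has its own rule: "For the last application, it is equal to 3".

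**14-day criteria.** SAP 6.2, in line with Protocol 9.4.2, admits to the FAS randomized subjects who "received at least 14 days of study drug for pituitary priming will be included in the FAS". Neither section cites a formula. SAP 4 uses 14 days of study treatment exposure to separate early discontinuation (withdrawal without an LH surge before that point) from women who count as completers once they have had the End-of-Study visit.

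**Progesterone after early stopping.** Protocol 3.1 limits the final-visit progesterone sample to one group: "For subjects who have discontinued the study early and ended treatment on or after Day 14, a blood sample will also be taken". The first scheduled post-baseline sample is on Day 19.

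**Delivery data.** Protocol 5.6.2: "The Manager records drug delivery data that may also be analyzed".

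**The concern.** The SAP is meant to add technical detail to the protocol. Here it replaces the protocol's stop date and time with an assumed 3 days of wear, and gives no reason.

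Treatment ends at menses, at the second confirmatory pregnancy test, or at discontinuation. None of these is tied to a pod change, so stopping mid-pod should be common. Every such woman gets too many exposure days. Because the last pod is set to 3 in both parts of the compliance ratio, removing it early can never lower compliance.

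The same assumption appears elsewhere in the SAP. Its treatment-emergent window runs to 5 days after the last application, while the protocol's runs to 2 days after the last dose. The two agree only if the last pod is worn for 3 days.

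The 14-day cut-offs raise the stakes. SAP 4 uses the term that 8.1.1 defines, and the FAS, which is the primary analysis set, leaves its day count unspecified. The SAP offers a programmer only two day counts, and both carry the 3-day credit.

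**Working it through.** The plan gives no figure to reproduce for this point, and no sample size, power or alpha figure depends on the formula. The check is day arithmetic.

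**Inputs.** Pods are due on Days 1, 4, 7, 10, 13 and so on, worn 3 days each (Protocol 5.1.1, SAP 3.1). The formulas are those of SAP 8.1.1, SAP 8.1.2 and Protocol 9.7. Assumptions: an earlier pod delivers until it is replaced or for 3 days, whichever is shorter; the last pod is worn 0 to 3 days; treatment stops when it comes off.

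**Formulas.**
- SAP 8.1.1: last − first + 3
- SAP 8.1.2: sum of min(next − current, 3), plus 3 for the last pod
- Protocol 9.7: stop − start = (last − first) + wear of the last pod
- Drug time: sum of min(next − current, 3), plus wear of the last pod

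| Pod days | SAP 8.1.1 | SAP 8.1.2 | Protocol 9.7 | Drug time |
|---|---|---|---|---|
| 1, 4, 7, 10 | 12 | 12 | 9–12 | 9–12 |
| 1, 4, 7, 10, 13 | 15 | 15 | 12–15 | 12–15 |
| 1, 4, 7, 10, 12 (one early change) | 14 | 14 | 11–14 | 11–14 |
| 1, 4, 10, 13 (one missed pod) | 15 | 12 | 12–15 | 9–12 |
| 1, 4, 13 (two missed pods) | 15 | 9 | 12–15 | 6–9 |

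**Exposure.** SAP 8.1.1 minus Protocol 9.7 equals 3 minus the wear of the last pod, so 0 to 3 days. If stop times were uniform over the last pod, the mean would be 1.5 days. For the on-schedule Day 13 case, 15 against 12 is 3/12 = 25% too high.

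**Compliance.** With no gap, the ratio is 15/15 under the SAP and 12/12 with real wear, so 100% either way. The credit changes the ratio only when there is also a gap. In the one-missed-pod case with immediate removal of the last pod, it is 12/15 = 80% under the SAP and 9/12 = 75% with real wear.

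**The 14-day cut.** On schedule, both SAP counts jump from 12 (last pod Day 10) to 15 (last pod Day 13). Either count would turn a 14-day rule into whether the Day 13 pod was applied. On actual times, a woman who stops less than 14 elapsed days after starting would fail it.

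**Outcome for the Day 13 stopper.** She ended treatment before Day 14, so no End-of-Study progesterone is required. Protocol 4.4 asks for that visit within 3 days of discontinuation (13 + 3 = Day 16), before the Day 19 sample. Under SAP 9.2.1 missing data count as no ovulation.

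**Size in the FAS.** Adding one failure to an arm of 14 with rate r lowers it by r/15:
- 20 µg: 0.70/15 = 4.7 points
- 15 µg: 0.65/15 = 4.3 points
- 10 µg: 0.60/15 = 4.0 points
- placebo: 0.01/15 = 0.07 points

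Going from 13 to 14 women, 9/13 to 9/14 is 69.2% to 64.3%, or 4.9 points. In the pooled 15 and 20 µg group, from 28 to 29 women, 0.675/29 = 2.3 points. At the first interim, 6/8 to 6/9 would be 8.3 points.

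**The case against.** **The FAS link is inferred.** SAP 8.1.1 states a descriptive use in the Safety Population, and neither FAS definition refers to it. A reader might infer that 8.1.1 decides FAS membership; the documents do not say so. This stands, and makes the FAS consequence conditional. What remains is that the FAS count is undefined and that SAP 4 does use the 8.1.1 term.

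**Gaps are not a conflict with the protocol.** A reader might say that ignoring lapses between pods departs from Protocol 9.7. It does not: start-to-stop duration ignores them too. SAP 8.1.2 already caps each gap and credits an early replacement with fewer days. This stands. Only the last-pod credit conflicts.

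**Very short exposures need unusual histories.** A reader might infer that women with as little as 9 days of drug pass routinely. Without gaps or early changes the minimum is 12. Reaching 9 takes a missed pod plus immediate removal of the last one, and 9 is not a floor either (two missed pods give 6 to 9). SAP 8.1.2 would count the one-missed-pod case as 12 and fail it. It does not rescue the on-schedule Day 13 case, which it also counts as 15.

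**The effect on the primary test is conservative.** Extra failures lower the active rates and barely move placebo, so they cannot favour the drug in the primary comparison. The mITT and ITT sensitivity analyses in SAP 9.2.1.2 do not use the 14-day cut. Both points stand. They do not cover the 20-point low-dose rule or the ED80 choice, which compare dose arms with each other, so an added failure can act in either direction.

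**Frequency is unknown.** The documents do not say how many women stop around Days 13 to 14. The planned stop for non-response comes after 21 full days.

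**Conclusion.** The concern holds in a limited form. It is certain that SAP 8.1.1 departs from Protocol 9.7 on the stop date, that exposure is overstated by 0 to 3 days for anyone who stops mid-pod, and that SAP 8.1.2 repeats the credit. It is also certain that the FAS has no stated counting method, while SAP 4 applies its cut to the quantity 8.1.1 defines.

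It is conditional on one of the two SAP counts being used for the FAS that an on-schedule woman with about 12 days of drug enters as 15 and is normally scored a failure. One such woman moves an active arm of 14 to 15 by about 4 to 5 points at the assumed rates of 60% to 70%. A reader might take one woman in 14 or 15 as about 7 points, but a failure added to the denominator costs that much only when the arm's rate is near 100%.

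This should be corrected before unblinding. It does not threaten type I error in the primary test.

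**What to change.** - **SAP 8.1.1:** compute exposure as the actual treatment stop date/time minus the start date/time, as Protocol 9.7 states.
- **SAP 8.1.2:** use the actual wear time of the last pod, from the diary or the last-dose date, with the Manager log where it was collected.
- **SAP 6.2 and SAP 4:** state that both 14-day criteria count days actually on drug, with gaps removed as 8.1.2 already does. Correcting 8.1.1 alone would not remove gaps.
- **End-of-Study progesterone:** the passages on the sampling trigger and on the 14-day rule must be reconciled. One refers to a study day and the other to an amount of drug; Day 14 at the starting clock time is 14 − 1 = 13 elapsed days.

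**Cost.** SAP wording and one derivation. Protocol 10.1 already requires first and last dose dates as source data, and pod replacement times are on the diary card. Collection of Manager data is optional under Protocol 5.6.2, so it can support the count but not carry it alone. Changing the sampling trigger itself would be a protocol change. Reported exposure will be slightly less favourable, as will compliance where there is also a gap, and a woman or two may leave the FAS.

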8.1.2 Treatment Compliance

Summary (descriptive) statistics will be presented for the number of OmniPods applied by each patient and the treatment compliance during the patient's actual treatment period, defined as the actual days of treatment exposure divided by the patient's total treatment exposure duration. The actual days of treatment exposure is the sum of the durations of individual applications. For each OmniPod application, the duration is calculated as: date of next application — date of current application, or 3, whichever is smaller. For the last application, it is equal to 3.

.

9 Efficacy

A Bayesian adaptive design is adopted to address the following objectives:

- 1. Demonstrate superiority of the pooled middle and high doses over placebo
- 2. Evaluate the dose-response relationship

The adaptive design includes two interim analyses, conducted after approximately 9 and 12 patients per arm enrolling in the study, respectively. Each interim analysis provides opportunities for stopping the trial early due to efficacy success utilizing the group sequential strategy or due to efficacy futility through Bayesian predictive probability of success. Furthermore, it allows the low dose to be dropped following the interim look if it shows a much lower response rate compared with the middle and high doses.

Each interim analysis will result in one of the following outcomes:

- 1. Continue the trial with all arms
- 2. Continue the trial without the low dose
- 3. Declare early success, but continue the trial without placebo
- 4. Declare early success and stop the trial (both placebo and low dose dropped)
- 5. Stop the trial for futility

When the primary efficacy analysis is not successful at the interim analysis, and if the ovulation rate in the low-dose arm is sufficiently low, satisfying

$$R_{low} \le (R_{high+middle}) - 0.2, \tag{1}$$

then the trial will continue without the low dose, resulting in outcome #2 above. Note that R_{low} and $R_{high+middle}$ in the inequality (1) above are the observed ovulation rates in the low dose arm and the combined middle- and high-dose arms, respectively. However, if inequality (1) is not satisfied, then the trial will continue with all arms (outcome #1).

Conversely, when success on the primary efficacy analysis is declared at an interim analysis, if the response rate in the low-dose arm meets the condition in inequality (1), then the trial is completed at this point (outcome #4) with dose selection performed using the ED80 rule (see below).

In the case the primary efficacy analysis is successful, but the response rate in the low-dose arm is within 20% from the combined low- and high-dose success rate, the trial is not stopped immediately. Rather, the trial will continue to enroll additional patients into the low-, middle- and high-dose arms to further assess dose responses (outcome #3).

Finally, the trial may terminate (outcome #5) as a result of a low predictive probability of success (<0.05) given the data collected at the interim analysis.

At the end of the study, for a trial that achieves efficacy success, the dose to be selected is the ED80 dose, defined as the lowest dose that retains at least 80% of the largest treatment effect, i.e.

$$(R_{ED80} - R_{placebo}) \ge (R_{maximum} - R_{placebo}) \times 0.8, \tag{2}$$

where $R_{maximum}$ is the observed ovulation rate in the most effective dose arm, $R_{placebo}$ is the observed ovulation rate in the placebo arm, and R_{ED80} is the observed ovulation rate in the selected dose arm.

A flow diagram is presented in Figure 1 of Section 15.2.1 to illustrate the decision tree for the two-interim adaptive design. Further details, such as the criteria for efficacy success using the group sequential method, the Bayesian predictive probability of future success to determine futility, the

rationales behind the 20% threshold to drop low dose, the ED80 dose-selection rule and dose-response evaluations are described in Section 9.2.1.1. Simulation results to assess operating characteristics of the design are given in Section 15.2.

9.1 General Considerations

Sites from all countries/regions (US, Canada) will be pooled for all analyses. No stratification by site will be made in the analysis.

Unless otherwise noted, data will be summarized in tabular format by treatment group using summary tables and data listings. All study data documented on the eCRFs will be included in the study data listings.

All efficacy analyses will be conducted for the FAS. The three placebo groups with different dose settings will be pooled as a single placebo group for all efficacy summaries and analyses.

Continuous variables will be described with the number of non-missing values, mean, standard deviation (SD), median, and minimum/maximum values. Categorical variables will be described with the number and percentage of subjects with each level. Missing values will not be included in the calculation of percentages. All individual subject data will be listed.

The software used for all summary statistics and statistical analyses will be SAS Version 9.2 or later.

